Hydrocephalus is a pathological condition that results from overproduction or under-absorption of cerebrospinal fluid (CSF) or obstruction of CSF flow pathways in the ventricle or subarachnoid spaces. It can be congenital (occurring in 4/1000 live births) or acquired due to intracranial haemorrhage, infection or tumours.

Hydrocephalus is often classified into:

- Obstructive (non-communicating)
 - Tumours (obstructing CSF pathways most commonly in the posterior fossa)
 - Congenital aqueductal stenosis
 - Fibroses of leptomeninges
 - Haemorrhage
 - infection
 - Dandy-Walker syndrome
 - Vascular malformations
 - Intracranial cysts (e.g. arachnoid cysts)
 - X-linked hydrocephalus
- Communicating (due to failure of CSF absorption into the venous sinuses)
 - Venous outflow obstruction
 - Venous thrombosis
 - Platybasia
 - Craniosynostotic syndromes
 - Down's syndrome
 - Leptomeningeal inflammation
 - Haemorrhage
 - infection
 - Trauma
 - Choroids plexus carcinoma (over-production)

In general the treatment of hydrocephalus involves that of the underlying cause (for example removing an obstructive tumour or cyst) but some form of CSF diversion is often required. The mainstay of such treatment since the early 1950's has been the use of the cerebrospinal fluid shunt where the excess CSF is drained by means of a valved tube from the ventricles to a body cavity where it could be reabsorbed. The commonest shunt since the 1970s has been the ventriculoperitoneal shunt (VP shunt). Shunts however, do have problems. Up to 50% of shunts will fail within a year of implantation due to blockage, fracture, migration, malposition and infection^{10,22}. Five to 10% of all newly implanted shunts can get infected⁴ and this has been shown to affect cognitive development¹¹. Shunts also have late complications and over 80% of shunts will have failed by 12 years (5). Other problems include overdrainage of the shunt and the slit ventricle syndrome. Alternatives to shunts have therefore been sought.¹⁹

Since the 1980's endoscopic procedures have been in use for the treatment of hydrocephalus¹⁷. The creation of a hole from the third ventricle through to

Is endoscopic third ventriculostomy an effective treatment in patients with hydrocephalus and cerebrospinal fluid shunt malfunction?

the subarachnoid space can allow CSF to bypass an obstruction, thus obviating the need for a VP shunt. The use of endoscopic third ventriculostomy (ETV) is now becoming more prevalent in the primary treatment of hydrocephalus particularly in cases of obstruction and a consensus of opinion exists regarding their high likelihood of success in these cases¹³. The use of ETV is also gaining popularity in the treatment of shunt malfunction even in cases where there was a communicating hydrocephalus to begin with. There are several papers advocating this (secondary ETV) as a worthwhile alternative to shunt revision. In some cases particularly in older patients ETV has been suggested as a treatment for shunt blockage in patients whose hydrocephalus was originally communicating^{3,5,7,9,20,25}.

In this unit we perform approximately 100 shunt revisions per year. In 2004, we performed 108 shunt revisions. In 47 of those cases (43.5%), a further procedure was needed because of complications with the new shunt. The 1-year survival revised shunts in 2004 was therefore 56.5%. There are series which show higher success rates (70%) with ETV following shunt failure²⁰. These are retrospective.

To date there has been no prospective analysis comparing ETV to shunt revision in patients who present with shunt problems requiring surgery.

Study objective:

The aim of this study is to compare the success rates of ETV and shunt revision in the treatment of shunt malfunction in patients with hydrocephalus, In other words to:

- determine which group of patients are most likely to require further surgery within a one year follow-up period
- To compare immediate complication rates between the two patient groups

Sample population:

All patients presenting to Leeds General Infirmary with shunt obstruction will be considered for the study regardless of the original cause of their hydrocephalus.

Inclusion criteria:

1. Symptoms/signs or radiological evidence of shunt obstruction
2. Ventricular anatomy making an endoscopic procedure feasible as judged by the attending consultant neurosurgeon:
 - a. Lateral and third ventricles adequate size
 - b. Thin third ventricle floor
 - c. Adequate pre-pontine cistern to fenestrate into with an endoscope
3. Age greater than one year

Exclusion criteria

1. Age less than one year (these children are less likely to benefit from ETV^{2,6,14-16,18,23,24})
2. Small ventricles preventing passage of the endoscope
3. Patients who would not be suitable for a shunt
4. Patients whose condition is such that urgent surgical intervention is needed and time for enrolment is not available
5. Patients who are unable to give consent and there are no available next-of-kin

Sample size:

In order to detect a statistical significant difference ($p < 0.05$) between the two groups we would require 196 patients at. The power calculations were performed by our IT department at Leeds General Infirmary ([name]). This unit performs surgery for approximately 100 patients per year with shunt malfunction and we would therefore calculate that the study will take four years to complete assuming about half of patients will not be suitable for the study or will not wish to take part.

Randomisation process:

We intend to randomise half of our patients to each arm of the study (i.e. 100 will have a shunt revision for their treatment and 100 will have an ETV). This will be done by choosing from a collection of 200 identically sealed envelopes kept in the theatre suite. For obvious reasons the surgeon and patient cannot be blinded to the treatment to which they are randomised.

Consent procedures:

For each patient presenting with shunt malfunction, the surgeon will assess whether they are suitable for the study. Once suitability has been confirmed, consent will be sought in three possible ways:

1. In the case of a patient under 16: The parents of the child will be given an information sheet detailing the reasons for, aims and methods of the study. In the case of a child who has a normal conscious level and is of an age where he/she can understand the study rationale, there is a specific information sheet for the child. A consent form will be signed by the registrar or consultant taking consent and the parents of the child (and the child where appropriate). A separate information for children who can read will be provided.
2. In the case of a consenting adult, with a normal conscious level: Information on the study will be provided as above and written consent obtained by the attending registrar or consultant.
3. In the case of an adult with reduced conscious level or who is mentally unable to comprehend the study: Consent will be sought from the patient's next-of-kin. Where there is no next-of-kin available, the patient will be excluded from the study.

Study procedure:

Before recruitment to the trial:

The patient who presents with symptoms or signs of shunt malfunction will have a thorough clinical examination, particularly neurological examination. Fundoscopy will be performed in all patients to ascertain the presence or absence of papilloedema. Where possible, a bedside visual field assessment and visual acuity test will be performed with a Snellen chart (competent older children and adults). Imaging will be performed as in all patients with suspected shunt malfunction:

- Shunt series of x-rays
- Cranial CT scan

These are not investigations exclusive to study patients but are performed routinely in such cases.

Where there is doubt as to the cause of the hydrocephalus or the suitability of the patient for ETV and the clinical condition of the patient allows the time a magnetic resonance imaging (MRI) study *may* be performed *prior* to consideration for study entry. This is done in most patients who have not had MR before as most patients presenting to us are assessed for suitability for ETV anyway. If the patient's condition is such that urgent surgery or other intervention is required, this intervention will take precedence over further investigation or entry into the study.

Once a patient is deemed suitable for trial, the patient/carer/parent/next-of-kin will be given information on the study and consent sought. Once written consent has been obtained, the patient is entered into the study. They will be given a study number and a proforma will be filled out. A sealed envelope will be opened to reveal the treatment arm and further consent for surgery will be obtained in the usual manner.

In the cases of those patients who present with shunt infection, they will not be considered eligible for the study until the infection has cleared. Treatment for shunt infection is by removal of the shunt, insertion of an external ventricular drain and administration of intravenous and intrathecal antibiotics for 10 days after the last positive CSF culture. Only at the point where a brand new shunt is considered would the patient be eligible for the study. Shunt infection is not a contraindication to ETV if infection is treated properly beforehand²³.

Those that are randomised to shunt revision will have part or all of the shunt replaced. Patients randomised to the ETV arm of the study may have the malfunctioning shunt left in situ. Once the patient has had their surgery, they will be kept in hospital until they are deemed well enough for discharge home. There will be a visual assessment prior to discharge.

Follow-up will be arranged for 6 weeks, 6 months and one year for all study patients. At the 6 week and 6 month clinic the patient will have a cranial imaging to assess ventricular size. Those that have had an ETV will have an MRI scan to determine patency of the stoma as well (this is normal practice

following such a procedure). If a shunt revision is performed, a CT or MRI will be performed. Fundoscopy and visual acuity are also assessed in clinic. This is no different from the normal follow-up of a patient who has had treatment of a blocked shunt.

Should a patient make an unscheduled presentation because of symptoms related to their hydrocephalus or surgery and recurrence of the hydrocephalus is suspected they will be investigated in the usual manner in such cases (i.e. clinical and/or radiological confirmation of failure of shunt or ETV if that is the case).

A final proforma will be filled in at the patient's exit from the study. Exit from the study can happen in 3 ways:

- The patient represents with shunt/ETV failure
- The patient is well at one year following surgery with no need for further surgical intervention
- The patient voluntarily withdraws from the study for any reason at all

Duration of the study

Subject to R&D and ethics committee approval, enrolment into the study will commence on January 1st, 2007 and we would expect to enrol the 200th patient by December 31st, 2010. To ensure a minimum of one years-follow-up, data accrual will continue for one year after recruitment of the 200th patient. Overall we would expect this study to last at most 5 years.

Treatment efficacy assessment/endpoints:

In each patient the following endpoints will be assessed:

Primary endpoint:

One-year success rate of the procedure (one-year survival of shunt or ETV)

- The procedure will be deemed a failure if the patient requires further surgical intervention within a year for treatment of their hydrocephalus. We felt that one-year follow-up was appropriate as most shunt and ETV failures occur in the first year following the procedure^{9,12}. The need for further surgery will be determined clinically or radiologically. In the case of patients who are in the ETV arm of the study, a sagittal MRI demonstrating the third ventricle floor will be sought where possible.

Secondary endpoints:

1. Occurrence of complications from surgery
2. Ventricular size changes
3. Length of inpatient stay
4. Number of re-attendances (excluding scheduled ones at 6 weeks, 3 months and 1 year) with symptoms related to their hydrocephalus/wound or implant.

Safety

Where either treatment would be deemed unsafe, the patient would be excluded from the study.

The risks of surgery are:

1. Death (less than 1% for shunt and ETV)
2. Epilepsy (approximately 5% short term risk in both treatments)
3. Minor vascular injury – Both treatments involve the passage of instruments through the brain to the ventricle. The risk of bleeding from this is about 5%. Most bleeds are sub clinical and don't result in neurological deficit. The risk of a bleed causing a deficit is about 1-2% for both treatments
4. Major vascular injury: This is a risk with ETV where basilar artery injury has occurred - death from it has been reported¹. However, most large series of patients treated with ETV, report no such injuries.
5. Infection: The shunt infection rate in this unit at present is 5%. The rate of CSF infection or ventriculitis is 0-10% in large series^{8,11,21} The rate of infection
6. CSF wound leak: This occurs in up to 5% of newly implanted shunt and is a high risk factor for infection. In the case of ETV it usually means that the ETV will not work and a shunt is needed²¹
7. Overdrainage and slit ventricle syndrome. This is a rare but serious problem in children treated with shunts. It can cause severe headaches and often requires further shunt surgery. It is not a recognised complication of ETV²²
8. Subdural haematomas. This is a complication seen with overdrainage of shunts in adults. It can mean that a patient will require surgery to remove the haematomas and shunt revision. It is also rarely seen with ETVs.

Subject withdrawal

Obviously, a patient or family can withdraw from the study at any point. If they withdraw at any point before the one-year follow-up, they will be excluded from analysis at the end of the study.

Is endoscopic third ventriculostomy an effective treatment in patients with hydrocephalus and cerebrospinal fluid shunt malfunction?

Data recording and proformas

All data will be recorded prospectively on proformas by one of the investigators:

There will be a proforma for

- The initial inpatient admission, surgery and discharge
- Follow-up proforma to be filled in at one year or earlier if treatment fails

Data storage:

All proformas will be kept in paper form by the principle investigator in his office and will be transferred onto a computer database on one desktop PC in the department of neurosurgery. This will be password controlled and only the named investigators will have access to it

ETV vs. Shunt Revision Study: admission

Hospital number 1

Surname First name Date of birth Date of entry into study

Admission details

Date of admission
 
Mode of presentation
 
 Self referral
 
 Through OPD
 
 GP
 
 Other hospital
 
 A&E
 
 Other...
	
Cause of hydrocephalus
 
 IVH
 
 Aqueduct stenosis
 
 Myelomeningocele
 
 Chiari malformation
 
 Tumour
 
 CSF infection
 
 Head injury
 
 Dandy Walker
 
 Craniosynostosis
 
 Venous thrombosis
 
 Unknown
 
 Other

---	---


Date of first shunt insertion
 
Date of last shunt revision
 
Number of previous revisions
 
Previous ETV? 
 
Site of ventricular catheter
 
 Frontal
 
 Parietal
 
 Occipital
 
 Other...
	
Type of shunt: Valve
 
Proximal catheter
 
Distal catheter
 
Antisiphon device  None  Integral  Separate
 
Rickham reservoir  None  Integral  Separate
 
Site of peritoneal catheter
 
 peritoneum
 
 heart
 
 pleura
 
 Other...

---	--

Symptoms
 
 Headache
 
 Nausea/Vomiting
 
 Irritability
 
 Lethargy
	
 New or changed seizures
 
 Diplopia
 
 Fever
 
 Developmental delay
	
 Deteriorating performance
 
 Abdominal symptoms
 
 Other...

--	--	---

Signs
 
 Fever
 
 Papilloedema
 
 Bulging fontanelle
 
 Increasing head circumference
 
 Decreased L.O.C.
 
 Nuchal rigidity
	
 Cranial nerve palsy
 
 Parinauds/Sunseting
 
 Focal deficit
 
 CSF leak
 
 Shunt reservoir not refilling
 
 Erythema over shunt
	
 Skin erosion/discharge
 
 Abdominal mass
 
 Peritonitis
 
 Delayed development
 
 Other...

---	--	--


Highest CRP
 
Highest WCC
	
ICP monitoring results
 
 not done
 
 inconclusive
 
 demonstrate shunt malfunction
	
Shunt tap
 
 not done
 
 unable to aspirate
 
 high pressure
 
 relieved symptoms
 
 demonstrated infection

---------------------------------------	---	---

Is endoscopic third ventriculostomy an effective treatment in patients with hydrocephalus and cerebrospinal fluid shunt malfunction?

ETV vs. Shunt Revision Study: discharge

Hospital number 1

Shunt xray not done migration
 normal Other...
 disconnection/fracture

CT scan not done
 enlarged temporal horns
 enlarged third ventricle
 enlarged frontal horns
 effacement of cortical sulci
 periventricular lucency
 increased ventricular size compared with baseline
 Enlarged 4th ventricle
 Aquaduct patent

MRI not done
 enlarged temporal horns
 enlarged third ventricle
 enlarged frontal horns
 effacement of cortical sulci
 periventricular lucency
 increased ventricular size compared with baseline
 Enlarged 4th ventricle
 Aquaduct patent

Surgery

Date of surgery

Findings Shunt infected (EVD intervening) Valve blocked
 Proximal block Overdrainage
 Distal block Other...

Procedure  Shunt revision
  Replacement of whole shunt  Replacement of proximal catheter  Replacement of distal catheter  Replacement of valve  Addition of ASD  Addition of reservoir	 ETV  ETV alone  ETV and EVD  ETV with VAD  ETV with lumbar drain  ETV and removal of original shunt  Other...
---	--

Complications

MRI prior to discharge not done
(in case of ETV) flow through stoma
 inconclusive
 no flow through stoma

Date of discharge

Is endoscopic third ventriculostomy an effective treatment in patients with hydrocephalus and cerebrospinal fluid shunt malfunction?

ETV vs. Shunt Revision Study: follow-up

Hospital number 1

Date of visit

CT during follow-up

- not done
- ventricle size decreased (normal)
- ventricle size decreased (still large)
- ventricle size unchanged (normal)
- ventricle size unchanged (still large)
- ventricle size increased
- Other...

MRI

- not done
- ventricle size decreased (normal)
- ventricle size decreased (still large)
- ventricle size unchanged (normal)
- ventricle size unchanged (still large)
- ventricle size increased
- flow through stoma (if ETV)
- Other...

Number of visits post discharge

Complications post-op	Free text
-----------------------	-----------

Status

- Functioning at one year
- Failed before one year
- Dead
- Lost to follow-up

Symptoms in successful patients

- none
- mild
- severe (requiring admissions)

Where failed: Date of failure

- Operation for failure
- shunt
 - ETV again
 - Other...

Cause of failure Free text

Statistical considerations:

The primary endpoints will be compared by a chi-squared test comparing success rates at one year in each group.

The timing of failure in those treatments that do fail will be compared using the Kaplan-Meier survival curves.

Complication rates are expected to be small and we expect no statistical difference in a study this size.

Mean numbers of reattendances and mean reduction in ventricular size will be compared using student's t-test

Data storage

All data will be stored on a PC and in paper form in the neurosurgical department.

Patients will be identified by their hospital numbers and only neurosurgical medical staff will have access to the data

Ethical considerations

There are no specific ethical issues in this study. Both treatments are well-recognised alternatives for managing patients with hydrocephalus

Publication of study findings

We plan to publish the results of this study in Journal of Neurosurgery

Presentations of the data will be made to at academic meetings (e.g. European Society for Pediatric neurosurgery and/or the International Society for Pediatric Neurosurgery)

2. Barlow P: Indications for endoscopic third ventriculostomy: a review of successful and failed cases. **British Journal of Neurosurgery** **11**:456, 1998

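### The stated requirement of 196 patients, used as the trial total, gives only about 50% power at the protocol's own success rates (56.5% vs 70%)

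*Protocol*

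**What the plan says.** The Sample size section says that, for a significant difference at p < 0.05 "between the two groups we would require 196 patients at". In the text available the sentence stops there. It gives no power, no target difference, no sidedness and no indication of per arm or total.

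The rest of the protocol treats the figure as a total. Under Randomisation process, "100 will have a shunt revision for their treatment and 100 will have an ETV", drawn from 200 envelopes. The Sample size section expects four years of recruitment at about half of 100 patients a year, and Duration of the study places the 200th patient at the end of 2010.

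The introductory text, just before the study objective, gives the only pair of rates for the two procedures in shunt malfunction. Of 108 revisions in 2004: "In 47 of those cases (43.5%), a further procedure was needed because of complications with the new shunt". Then: "The 1-year survival revised shunts in 2004 was therefore 56.5" (per cent). For the other arm: "There are series which show higher success rates (70%) with ETV following shunt failure". The protocol notes that those series are retrospective.

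Statistical considerations fixes the primary test as a chi-squared comparison of one-year success. Subject withdrawal removes from the analysis anyone who withdraws before one year.

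**The concern.** A sentence that says how many patients are required to detect a difference will be read as an assurance that the trial is large enough. The difference that motivates this trial is 56.5% against 70%, or 13.5 points. If the planned total has only an even chance of detecting it, the assurance is wrong for the effect the protocol itself puts forward. A real ETV advantage of that size would give a non-significant test about half the time, and a reader who trusted the sample size statement could take that as evidence that the procedures perform alike.

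**Working it through.** **Inputs from the protocol.** Shunt revision success p1 = (108 − 47)/108 = 61/108 = 0.5648, printed as 56.5%. ETV success p2 = 0.70. Significance level 0.05. Allocation 1:1 with 100 per arm, or 98 per arm if 196 is the total. Primary test: chi-squared.

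**Assumptions.** The test is two-sided (z = 1.960). Where a target power is needed, it is 80% (z = 0.8416). The design rates are the background pair. The protocol states none of these as a design assumption.

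**Step 1: where 196 could come from.** With p1 = 61/108, the difference d is 0.1352 and d² = 0.018275. The unpooled variance sum is V = 0.2458 + 0.2100 = 0.4558. The mean rate is 0.6324, so the pooled term is P = 2 × 0.6324 × 0.3676 = 0.4649.

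- (a) 80% power, unpooled: n per arm = (1.960 + 0.8416)² × V / d² = 7.849 × 0.4558 / 0.018275 = 195.8, so 196 **per arm**. With the printed 0.565 it is 196.3, so 197.
- (b) 80% power, pooled: n per arm = (1.960√P + 0.8416√V)² / d² = 198.5, so 199. With 0.565 it is just above 199, so 200.
- (c) Significance only, pooled, no power term: n per arm = 1.960² × P / d² = 3.8415 × 0.4649 / 0.018275 = 97.7, so 98 per arm and 196 **in total**. With 0.565 it is 97.99, again 98 and 196.

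Both (a) and (c) reproduce 196, the first as a per-arm number and the second as a total.

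**Step 2: power of the planned total.** Here p1 = 0.565, d = 0.135, √P = 0.6818 and √V = 0.6751. Power = Φ[(d√n − 1.960√P)/√V].

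- n = 98: (1.3364 − 1.3364)/0.6751 ≈ 0, so power is 50.0%.
- n = 100: (1.3500 − 1.3364)/0.6751 = 0.020, so power is 50.8%.

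Exact binomial enumeration of the chi-squared test, with rates 0.565 and 0.70:

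| Per arm | Uncorrected | Continuity-corrected |
|---|---|---|
| 98 | 49.6% | 43.9% |
| 100 | 50.9% | 44.8% |
| 196 | 79.8% | 76.7% |
| 200 | 80.3% | 77.4% |

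With 61/108 in place of 0.565, the uncorrected figure at 100 per arm is 51.0%.

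**Step 3: what the planned total can detect.** With 100 per arm and 56.5% for revision, 80% power needs an ETV rate of about 75.2%, a difference of 18.7 points. With 98 per arm it needs 75.4%, or 18.9 points.

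**Step 4: precision.** The expected 95% CI half-width at 100 per arm is 1.960 × √(0.4558/100) = 0.132. That is about 13 points, much the same as the 13.5-point difference.

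**Step 5: withdrawals.** The protocol gives no rate. If 10% to 20% were lost (an assumed range), 90 or 80 per arm would remain, with power of about 47% or 42%.

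**Step 6: size for 80% power.** From (a) and (b), 196 to 200 per arm, which is 392 to 400 in total before withdrawals. At about 50 patients a year that is about eight years (400/50), against the four planned.

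**The case against.** A reader might infer that the sponsor computed 196 per arm and mistook it for the total. The documents do not establish that. The match in (a) needs the unpooled formula, the unrounded 61/108 and an assumed 80% power. The significance-only calculation in (c) gives 196 as a total, and it fits a sentence that, in the text shown, names a p-value and no power. On that origin nothing was mislabelled; power was left out. The missing words after the break may be a loss in reading the file and cannot be held against the plan.

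Nor is 56.5% vs 70% named as the design effect. The 70% is background from retrospective series, and the 56.5% covers all 2004 revisions, whereas the trial takes only patients whose anatomy suits ETV. Other assumptions also give a total near 196: 56.5% vs about 75.4% at 80% power, two-sided; or 50% vs 70%, one-sided at 90% power (198, unpooled). The protocol does say that up to half of shunts fail within a year of implantation, but that is an upper limit for implanted shunts generally. At two-sided 5% and 80% power, 50% vs 70% needs 182 to 186 in total (206 with continuity correction), which does not match. The protocol states neither alternative as its basis.

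It is also fair that the statement as shown promises no particular power, and that the protocol plans no equivalence conclusion on the primary endpoint.

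All of this limits what can be said about the cause. None of it alters the power of 98 to 100 per arm at 56.5% vs 70%, which follows from the rates, the test and the numbers whichever way 196 was obtained.

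**Conclusion.** The point holds as a statement about power, not about origin. The protocol gives 196 as the number required and plans 200. At its only paired rates for the two procedures this gives about 50% power (44% to 45% with continuity correction), and 80% power would take roughly twice as many patients. A per-arm number used as the total and a calculation without a power term are both consistent with 196, and the text shown does not settle which applies.

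The 50% figure rests on two assumptions: a two-sided test, and 56.5% vs 70% as the difference of interest. If the test were one-sided at 5%, power would be 62% to 63%, still well short of 80%. The 80% level serves only as the benchmark for the 392 to 400 patients and for the detectable difference of about 19 points.

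**What to change.** Correct the Sample size section so that it:

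- states the two assumed success rates, the power, the sidedness, and whether 196 is per arm or total;
- says that 200 patients (100 per arm) give about 50% power for 56.5% vs 70%, and about 80% power only for 56.5% vs about 75% (about 19 points);
- says that 80% power for 56.5% vs 70% would need about 196 to 200 per arm (392 to 400 in total) before withdrawals.

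If 196 was derived from other rates, the section should give and justify them. It should not assert an origin for the figure that the sponsor cannot confirm.

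Report the difference in one-year success with its 95% CI (expected half-width about 13 points), and state that a non-significant test will not be read as showing no difference.

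The cost is a few lines of wording and a less favourable stated detectable difference. The correction needs no extra patients.

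### Envelopes are drawn in no fixed order from an unnumbered set, so nothing ties the first envelope opened to the patient and a redraw would not show in the planned records

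*Protocol*

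**What the plan says.** The Randomisation process section plans equal arms ("100 will have a shunt revision for their treatment and 100 will have an ETV") and gives the method: "This will be done by choosing from a collection of 200 identically sealed envelopes kept in the theatre suite". It adds: "For obvious reasons the surgeon and patient cannot be blinded to the treatment to which they are randomised".

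Under Consent procedures, when a patient presents, "the surgeon will assess whether they are suitable for the study". The Study procedure section then sets the order of events. Entry follows consent: "Once written consent has been obtained, the patient is entered into the study". Numbering and paperwork come next: "They will be given a study number and a proforma will be filled out". Only after that: "A sealed envelope will be opened to reveal the treatment arm and further consent for surgery will be obtained in the usual manner".

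The primary endpoint is one-year success, and failure means further surgery for hydrocephalus within the year. On how that is judged, the endpoints section says: "The need for further surgery will be determined clinically or radiologically".

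**The concern.** Once an envelope has been opened, the allocation should be final, and a departure from it should be visible. The protocol provides neither property. It describes a draw from a set, not the next item in a series, and links no envelope to a patient. If the first envelope opened is unwelcome, it can be put aside or put back and another taken, and the planned records would look the same as after a first draw.

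This matters because the people concerned have prognostic information beforehand. Ventricular anatomy is judged before entry, MRI may be obtained before entry where the cause or suitability is in doubt, and cause of hydrocephalus is an item on the admission proforma. The Protocol's background also reports a consensus that primary ETV is likely to succeed in obstructive cases, while patients are considered whatever the original cause. If patients thought likely to do well were redrawn towards ETV, and others towards shunt revision, the chi-squared comparison of one-year success would partly measure who was sent to each arm. Treatment is open and re-operation involves clinical judgement, so sound allocation is one of the few protections left to this trial.

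**Working it through.** **Reading the allocation path**

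| Step | What the Protocol provides | What is absent |
|---|---|---|
| Suitability | Judged by the surgeon before consent | – |
| Entry | Consent, entry and study number precede opening | A link from study number to envelope |
| Draw | Any one of 200 identical sealed envelopes | Numbering, fixed order, named custodian or opener |
| Opening | One envelope is opened to show the arm | Labelling with the patient's identity beforehand |
| Record | Discharge proforma: procedure performed | Envelope number and allocated arm, on any proforma shown |
| Check | None described | Log; reconciliation of used envelopes with patients entered |

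The count itself is consistent: 100 + 100 = 200 envelopes, enough for the 196 patients required under Sample size.

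**How large could the effect be?** The Protocol gives no figure for this, so what follows is an illustration.

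Input from the Protocol: one-year success of revised shunts 56.5% (background). Assumptions: 100 patients per arm; no true difference; half the patients have good prognosis (71.5% success) and half poor (41.5%), so the mean is (71.5 + 41.5)/2 = 56.5% and the gap is 30 points; prognosis acts equally in both arms; in a fraction f of patients one redraw is made if the first envelope is unwelcome, towards ETV for good prognosis and towards shunt revision for poor.

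1. Chance that a steered patient ends in the preferred arm: 0.5 + 0.5 × 0.5 = 0.75.
2. P(ETV | good) = 0.5(1 − f) + 0.75f = 0.5 + 0.25f, and P(ETV | poor) = 0.5 − 0.25f.
3. Success in the ETV arm = (0.5 + 0.25f) × 0.715 + (0.5 − 0.25f) × 0.415 = 0.565 + 0.075f. In the shunt arm it is 0.565 − 0.075f. Spurious difference = 0.15f.
4. Standard error = √(2 × 0.565 × 0.435/100) = 0.0701. With z = 0.15f/0.0701, the two-sided type I error is 1 − Φ(1.96 − z) + Φ(−1.96 − z).
5. Extra envelopes opened over 200 patients = 200 × f/2, because half of the first draws in steered patients are unwelcome. If these are set aside and not returned, the set lasts for about 200/(1 + f/2) patients.

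| f | Spurious difference (points) | Type I error | Extra envelopes | Set lasts for (patients) |
|---|---|---|---|---|
| 10% | 1.5 | 5.5% | 10 | 190 |
| 20% | 3.0 | 7.1% | 20 | 182 |
| 30% | 4.5 | 9.8% | 30 | 174 |
| 50% | 7.5 | 18.8% | 50 | 160 |

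**Sensitivity.** If prognosis affects ETV success only and every shunt patient has 56.5%, the shunt arm does not move and the difference halves to 0.075f. That is 0.75 to 3.75 points over the same range of f, with type I error of 5.1% to 8.3%.

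**The case against.** The best defence is the order of events. The patient is consented, entered and numbered before any envelope is opened, so nobody can decide on enrolment after learning the arm. That stands, and it closes the commonest route to selection bias.

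Several stronger readings are tempting, but the Protocol does not support them.

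- **That surgeons can pick the arm they want.** The envelopes are sealed and identical, so choosing among intact ones reveals nothing. Opacity is not stated, but neither is its absence. The exposure is opening one and drawing again.
- **That the surgical team has free access.** The Protocol does not say who draws or who can reach the set. Access is an inference from the storage place and the lack of a named custodian.
- **That redrawing would leave no trace at all.** The set is exactly 200, so frequent discarding would exhaust it early, as the last column of the table shows. Only resealing and returning envelopes would avoid this. The fair statement is that no check is planned, and light discarding or return could go unnoticed.
- **That the bias must be large.** Exchanging 10 patients with 80% success for 10 with 40% would shift each arm by 10 × (0.80 − 0.40)/100 = 4 points, 8 in total. Those rates are not in the Protocol. Such a swap needs 20 reversed allocations and, at about one success in two redraws, about 40 discarded envelopes.
- **That nothing could be done at analysis.** Cause of hydrocephalus, number of previous revisions and previous ETV are recorded at admission, so imbalance on these could be seen and partly adjusted for. Unrecorded judgement could not.
- **That lack of blocking or stratification is an error.** Using up a 100/100 set gives final balance, and a large unblocked set is hard to predict. This is a trade-off.

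The inclusion criteria on ventricular anatomy also narrow what is left to steer on. None of this prevents an envelope from being replaced after it has been opened.

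**Conclusion.** The point holds in a limited form. The Protocol itself fixes a weak allocation procedure, and a later analysis plan could not repair it: the envelope opened first is not bound to the patient, the allocated arm is not recorded apart from the operation performed, and no reconciliation is planned. The decision to enrol is protected; the allocation is not.

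The consequence cannot be sized from the documents. On the assumptions stated, the spurious difference runs from 1.5 to 7.5 points and the type I error from about 5.5% to 19% as steering rises from 10% to 50% of patients, and the differences halve if prognosis matters only for ETV. For scale, the background rates of 70% and 56.5% differ by 13.5 points. If redrawing is rare the harm is small, but the records as planned could not show whether it was rare. The text gives no ground for supposing that redrawing is intended or likely. The defect is that it would be possible and probably undetected.

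**What to change.** Amend the Randomisation process and Study procedure sections, and the admission proforma, as follows:

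- Have someone who neither recruits nor operates prepare sequentially numbered, opaque sealed envelopes from a computer-generated list.
- Always take the next number. Write the study number, date and time on the envelope before it is opened.
- Record the envelope number and allocated arm on the admission proforma, separately from the procedure performed on the discharge proforma.
- Reconcile opened envelopes with the enrolment register, and account for every number.

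The cost is a few hours of preparation, a short amendment and slightly less convenience at the time of allocation. Sample size and treatment are unaffected. Blocking, or stratifying by type of hydrocephalus, may be considered but is optional.
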